### Study Protocol with Statistical Analysis Plan

Scientific Background: Sleep disturbance is the most commonly endorsed symptom among Veterans with PTSD1, and obstructive sleep apnea (OSA; 47%) and insomnia (26%) are the most common diagnoses among Veterans with any sleep disorder. The first-line treatment for OSA is positive airway pressure (PAP), which forces air into the airway while the patient is asleep to prevent upper airway collapse. PAP use results in reductions in daytime sleepiness and improvements in functioning and quality of life. Among those with PTSD, PAP use is associated with reduction in overall PTSD symptom severity.6- However, PAP adherence rates are notably low among those with PTSD. In addition, PAP use alone may not be sufficient in resolving quality of life/sleep-related functioning among those with PTSD, likely due to the comorbid insomnia that many patients experience. Both the American College of Physicians and American Academy of Sleep Medicine's guidelines for the management of chronic insomnia recommend Cognitive Behavioral Therapy for Insomnia (CBT-I) for insomnia as a first-line intervention. 11,12 In spite of frequent comorbidity, little is known about the outcome of CBT-I in those with sleep apnea because they are usually excluded from trials. Furthermore, insomnia itself is associated with PAP non-adherence. By offering a behavioral intervention that reduces insomnia and addresses PAP adherence at the initiation of care for sleep apnea, Veterans may have greater success in adhering to treatment and realizing symptom and functional improvement. Furthermore, there is no integrated approach to treating Veterans with OSA and insomnia concurrently, but rather only through a piecemeal sequence, which is often uncoordinated between different treatment clinics and across a prolonged timeline. The proposed project allows for the evaluation of a treatment that addresses sleep apnea and insomnia in tandem and within the context of PTSD.

Objective: Aim 1: Conduct a pilot RCT comparing AIR (n = 40) with sleep education (control condition; n = 40) for Veterans with OSA, insomnia, and PTSD. Hypothesis 1a: Veterans receiving AIR will demonstrate improved quality of life (WHOQOL-BREF; primary outcome) and functioning (FOSQ-10; secondary outcome) compared with control at post-treatment and follow-up assessments. **Hypothesis 1b**: Veterans receiving AIR will demonstrate greater reduction in symptoms of insomnia (ISI and actigraphy) and PTSD (CAPS-5), and greater adherence to PAP (device data capture) compared with control at post-treatment and follow-up.

Aim 2: Evaluate the feasibility and acceptability of AIR. Participants will complete a Feasibility and Acceptability Questionnaire (FAQ) and follow-up interview based on their questionnaire responses. Topics will include content of treatment as well as experience completing the treatment delivered via telehealth. Examination of treatment dropout and attendance at other PAP-related appointments will also be monitored to determine whether the treatment facilitated increased engagement in care. Hypothesis 2a: Veterans receiving AIR will report at least moderate agreement with items on the FAQ. Hypothesis 2b: There will be lower dropout in the AIR condition compared with control. Hypothesis 2c: There will be greater engagement in apnea care in the AIR condition compared with control

**Aim 3 (Exploratory): Evaluate moderators of treatment outcome.** I will evaluate the data for trends indicating potential moderators of treatment outcomes, such as sleep apnea severity or concurrent medication use.

Design: First, I will conduct a randomized controlled trial of AIR and a sleep education control condition. The primary outcome will be quality of life. Next, I will solicit Veteran feedback to assess the feasibility and acceptability of AIR and evaluate measures of engagement in care. Finally, I will identify moderators of treatment outcome, which may help target Veterans for whom the treatment needs further refinement.

### **Methods:**

Recruitment Procedures. After Veterans receive a referral for sleep apnea testing, research staff will send a letter inviting them to participate in the research study and notifying them that they will be contacted by study staff if we do not hear from them within 2 weeks opting-out. Veterans will have the option to opt-out via phone or email information provided in the letter. Veterans may also be contacted via invitation letter at the point of sleep apnea diagnosis and/or after review of PAP data demonstrating non-adherence to PAP. If a Veteran returns an interest in research form as part of their sleep apnea testing questionnaire packet and indicates they are interested in research, study staff may reach out via phone. Additionally, VA healthcare providers may refer their patients to the study if Veteran agrees to be contacted by research staff. This verbal consent to contact will be documented in the medical record. VA providers will refer patients through secure methods of notification, such as encrypted email, alert in medical record, and/or through a phone call. If VA healthcare providers give the Veteran approved informational brochure or flyer, the Veteran may also directly contact study staff. Veterans may also be identified as potential study participants via chart review prior to other VA appointments, such as appointments in PTSD clinic, to allow for identification of Veterans who may be eligible but are either not yet connected to VA sleep care or were previously connected but no longer engage in sleep care.

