### **Data Collection Procedures.**

**Screening.** Veterans will become eligible for initial screening following referral for sleep apnea testing. Sleep apnea testing is routine clinical care. The Research Assistant will contact potential participants to complete a phone screening. For those interested, the RA will obtain verbal consent to screen the potential participant for initial eligibility and inform participants that questions may address traumatic experiences and reactions. The screening questions will consist of basic contact information, insomnia symptoms, and PTSD symptoms. The screening will also establish any recent or upcoming changes to PTSD or sleep treatment aside from potential treatment for sleep apnea via the Sleep Clinic, as well as screen for exclusion criteria of recent substance use disorder, psychosis or manic episode within last 5 years, acute suicidality requiring alternate treatment, night shift or rotating shift work, lack of stable housing, and pregnancy. \*This is solely for research purposes.

If the Veteran's sleep study took place in 2018 or earlier, we will obtain their weight at time of sleep apnea testing from the medical record and ask the Veteran their current weight. We will also ask them if they currently snore loudly, feel fatigued during the day, have been recently observed to stop breathing while they sleep, and have a history of hypertension. We will then send this information to a SFVA Sleep Medicine provider via encrypted email who will determine if this Veteran would benefit from an updated sleep apnea test and/or other clinical care prior to enrollment in this study. This will facilitate routine clinical care. Consent. Potential participants deemed initially eligible via phone screen will be invited to attend a consent appointment via phone or video. Prior to the appointment, the consent document will be sent via mail, Secure Messaging on MyHealtheVet (if the Veteran has a printer) or email. The RA will review the consent document with the Veteran and emphasize that participation in the study is voluntary and the Veteran's choice to participate or not will not affect their eligibility for standard care in VA. The Veteran will sign a written consent form and return to study staff.

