Clinical interview. Trained clinical interviewers will conduct the CAPS-5 interview to establish PTSD diagnosis and SCID-5 interview to establish insomnia diagnosis. This will take place over phone or video. The SCID-5 will also be used to rule out diagnostic exclusion criteria and establish comorbid mental health conditions for data analytic purposes. A brief medication interview will be conducted to obtain information about recent and current medication use. Interviews will be audio-recorded and reviewed by the Stress and Health Research Program's clinical assessment supervisor \*This is solely for research purposes.

Baseline prospective sleep data. Once eligibility is established, the Veteran will be shown how to complete a sleep diary. He or she will then record one week of baseline sleep data. Research staff will email the Veteran a link to enter sleep diary data via Qualtrics. The Veteran's PAP setup appointment (if needed) and treatment schedule will be planned. \*This is for research purposes; however, please note that completing a sleep diary is also part of routine care.

**Actigraphy.** The actigraph is a device worn on the risk to measure time asleep vs. awake. A subset of participants will be asked to wear the actigraph. The information will be used solely for research purposes. It is not part of the treatment.

**Baseline appointment**. The Veteran will complete pre-treatment measures. He or she will be randomized to either AIR or SE. \* Many of the pre-treatment measures are completed as part of routine care, but some are added for research purposes.

**Randomization procedure.** A block-randomization procedure will be used to assign participants to AIR or SE in a 1:1 ratio. Block sizes will be a random permutation of 4 and 6. Statistical consultant [REDACTED] will produce the computer-generated list. Each therapist will have his or her own randomization list. The randomization to treatment is for research purposes.

**Weekly assessment.** At the start of each treatment appointment, the Veteran will complete two self-report questionnaires assessing sleep (ISI and ESS). The Veteran's PAP adherence data and actigraphy data will also be downloaded or requested verbally. A copy of the Veteran's sleep diary will be obtained. At his or her final treatment appointment, the Veteran will be asked to complete a sleep diary to submit at the Post-Treatment

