#### **Exploratory Analyses.**

5.0 will be considered acceptable.

**Evaluation of moderators of treatment outcome:** We will evaluate the data for potential moderators of treatment outcomes. This will facilitate adjustments to the protocol prior to a large-scale RCT.

**Analyses:** We will evaluate interactions between subject characteristics and treatment effects to generate hypotheses for informing future work. This exploratory process is necessary because the sample size in the proposed project is insufficiently powered for multiple formal subgroup analyses. In these exploratory analyses, the focus will be on estimated effect sizes rather than statistical significance. These will be calculated based on interaction terms in the models described under Hypothesis 1a above. The primary

moderators of interest are: AHI, concurrent use of sedative-hypnotic medication, baseline PAP self-efficacy (SEMSA), baseline daytime sleepiness (ESS), and baseline sleep quality (PSQI). We will also examine demographic variables and comorbid medical or psychiatric conditions

**Secondary treatment outcomes:** Veterans receiving the behavioral sleep treatment will demonstrate greater increase in sleep efficiency (sleep diary), greater reduction in daytime sleepiness (ESS), greater reduction in PTSD symptom severity (PCL-5), greater improvement in sleep quality (PSQI), and greater improvement in self-efficacy in using PAP (SEMSA) compared with control at post-treatment and follow-up assessment.

**Analyses:** SEF will be the primary variable of interest derived from sleep diaries. The ESS is administered at pre-treatment, sessions 1-6, and post-treatment. The PCL-5, SEMSA, and PSQI are completed at baseline and post-treatment. Separate linear mixed models as described for primary hypotheses 1a and 1b will be estimated for each measure, with each secondary outcome hypothesis tested by the significance of the group difference in baseline-adjusted marginal mean scores post-treatment. Standardized effect sizes will be calculated as the marginal post-treatment group differences divided by pre-treatment standard deviations.

**Evaluation of global treatment satisfaction:** We will examine CSQ-8 total scores for evidence of treatment satisfaction. We will evaluate the data for group differences in treatment satisfaction.

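### New PAP setups and Veterans with earlier PAP or sleep care are enrolled together, but this pre-randomization distinction is neither a covariate in the PAP-hours model nor a named moderator

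*Combined protocol and SAP*

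**What the plan says.** The Scientific Background argues for an intervention that "addresses PAP adherence at the initiation of care for sleep apnea". Recruitment Procedures is broader. Besides Veterans referred for testing or newly diagnosed, it allows an invitation "after review of PAP data demonstrating non-adherence to PAP", and chart review may find Veterans who "were previously connected but no longer engage in sleep care".

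The plan recognises the distinction twice. Under Baseline prospective sleep data, before the baseline appointment at which randomization takes place: "The Veteran's PAP setup appointment (if needed) and treatment schedule will be planned". Under Engagement in follow-up care, the comparison of attendance at the return visit (Hypothesis 2c) is confined to Veterans whose PAP was newly set up during the study.

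It does not appear elsewhere:

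- **Phone screen.** "The screening questions will consist of basic contact information, insomnia symptoms, and PTSD symptoms", plus exclusions and a question on "any recent or upcoming changes to PTSD or sleep treatment aside from potential treatment for sleep apnea via the Sleep Clinic". PAP history is not listed.
- **Randomization.** One permuted-block list per therapist, with no other factor.
- **PAP-hours model (Analyses for PAP adherence).** The ISI model is reused for mean PAP hours over the preceding week. Measurement begins at session 1.
- **Moderators (Exploratory Analyses).** The primary "moderators of interest are: AHI, concurrent use of sedative-hypnotic medication", followed by SEMSA, ESS and PSQI. Demographics and comorbid conditions may be added. PAP status is not named.

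**The concern.** Veterans starting PAP and Veterans who already have a device, or have left sleep care, may well differ in nightly hours whichever arm they are in. A baseline variable that predicts the outcome and is known before randomization is normally put in the model. Leaving it out costs precision and lets a chance imbalance between two arms of 40 move the estimate.

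The usual safeguard is a pre-treatment value of the outcome, and here it is not secured. The ISI model that PAP hours borrows has a pre-treatment covariate, and the effect size is divided by a pre-treatment SD, yet no PAP measurement before session 1 is described. According to the intervention section, the device is typically handed over on the day of session 1, so a new user has no earlier use. A lapsed user may also show zero for the preceding week, so a session 1 value would not reliably separate the two.

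The second loss concerns the purpose of the pilot. Its results are meant to shape a full-scale trial. Whether that trial should enrol at PAP setup, after non-adherence, or both is a design question that this recruitment plan raises and the analysis plan does not report on.

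**Working it through.** **No figure to reproduce.** The documents give no share of prior users, no SD for PAP hours and no expected difference in use. The sizes below therefore rest on assumptions and apply to PAP hours only.

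**Inputs**
- n = 40 per arm, N = 80 (Objective, Aim 1).
- p, share of prior users: assumed 0.3 to 0.5.
- Within-group SD of PAP use: assumed 2.5 h, variance 6.25.
- D, difference in nightly use between prior and new users: assumed 1, 2 or 3 h.
- No adjustment for earlier use.

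**Chance imbalance.** SD of the between-arm difference in the share of prior users = sqrt(p(1-p) × 2/40).
- p = 0.3: sqrt(0.21 × 0.05) = 0.102.
- p = 0.5: sqrt(0.25 × 0.05) = 0.112.

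**Shift in the arm difference** for a 1.96-SD imbalance = 1.96 × SD × D.

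**Gain from adjustment.** R² = p(1-p)D² / (p(1-p)D² + 6.25). The standard error is multiplied by sqrt(1 - R²).

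| D (h) | p | Shift (h) | R² | Fall in standard error |
|---|---|---|---|---|
| 1 | 0.3 | 0.20 | 0.033 | 2% |
| 1 | 0.5 | 0.22 | 0.038 | 2% |
| 2 | 0.3 | 0.40 | 0.118 | 6% |
| 2 | 0.5 | 0.44 | 0.138 | 7% |
| 3 | 0.3 | 0.60 | 0.232 | 12% |
| 3 | 0.5 | 0.66 | 0.265 | 14% |

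Example, D = 2 and p = 0.5: shift = 1.96 × 0.112 × 2 = 0.44 h; R² = 1.00/7.25 = 0.138; sqrt(0.862) = 0.93.

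**How often imbalance arises.** A 1.96-SD imbalance is an uncommon draw, so smaller ones are also relevant. From the hypergeometric distribution (80 Veterans, 40 per arm):

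| Prior users | Gap of at least 15 points | Gap of at least 20 points |
|---|---|---|
| 20% | 16% | 5% |
| 35% | 24% | 10% |
| 50% | 26% | 12% |

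**What a moderator estimate could show.** In units of the within-group SD, standard error of the interaction = sqrt((4/80)(1/p + 1/(1-p))).
- p = 0.20: 0.559, 95% half-width 1.10 SD.
- p = 0.35: 0.469, half-width 0.92 SD.
- p = 0.50: 0.447, half-width 0.88 SD.

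Such an estimate is descriptive only, which fits the plan's stated emphasis on effect sizes for moderators.

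**The case against.** The best defence is that the trial is broad by intent. Aim 1 defines its population by the three diagnoses, without limiting it to new PAP users. The background also rests on poor PAP adherence in PTSD and on the lack of integrated care. No hypothesis claims an effect at the start of apnea care. All of this stands: the recruitment routes sit uneasily with one clause of the rationale, but they break no eligibility rule.

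Second, the plan already has relevant provisions. Hypothesis 2c uses new-setup status, so the team must be able to identify it. The SAP also lets baseline variables with large imbalances enter a sensitivity analysis. That stands in part. The provision does not name PAP status, does not define large, and acts only after the imbalance is seen. The adherence levels and the non-adherent subset later in the SAP describe use during the study, not status at entry.

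Third, the sizes are assumed, concern one Hypothesis 1b outcome, and say nothing about the WHOQOL-BREF primary outcome. This stands, and it keeps the point modest.

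A reader might go further, but the documents do not support these inferences:
- **That good PAP users will enter.** This rests on silence. The text has no full inclusion list and does not itemise the pre-treatment measures. For the same reason, it cannot be said that PAP history goes unrecorded.
- **That moderation by SEMSA would merely reflect PAP history.** The documents describe SEMSA only as PAP self-efficacy, so this is conjecture.
- **That the second group has failed PAP.** The text speaks of non-adherence and of leaving sleep care; the latter need not involve a device.

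**Conclusion.** The point holds as an inexpensive improvement, not as a flaw that invalidates the trial. A reader might infer that mixing the groups biases the AIR versus sleep education comparison. It does not: randomization protects that comparison in the mixed sample. The loss lies in precision and exposure to chance imbalance for PAP hours, and in a pilot that does not report on a split relevant to the next trial.

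Under the assumptions stated, the size ranges from minor (about 0.2 h and 2% of the standard error for a 1 h difference in use) to worthwhile (up to 0.66 h and 14% for 3 h). If the PAP-hours model were given a baseline value that captured earlier use, these figures would shrink.

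**What to change.** 1. Before randomization, record PAP status at entry in two levels: new setup, or prior or current device. Report it by arm. No adherence threshold is needed, and the plan defines none for entry.
2. Enter it as a pre-specified fixed covariate in the Hypothesis 1b PAP-hours model. State what serves as the pre-treatment PAP value for each group, or that there is none.
3. Add it to the moderators under Exploratory Analyses. Report estimates with intervals, labelled exploratory.
4. Rest any statement about benefit at the start of apnea care on the new-setup estimate.

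The cost is one data field, SAP wording, and one or two degrees of freedom. Randomization is unchanged. The drawback is imprecise subgroup estimates: an interaction half-width of about 0.9-1.1 SD at N = 80 if 20-50% are prior users, too wide to show on its own that the effect differs or does not.

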### **Data Collection Procedures.**

**Screening.** Veterans will become eligible for initial screening following referral for sleep apnea testing. Sleep apnea testing is routine clinical care. The Research Assistant will contact potential participants to complete a phone screening. For those interested, the RA will obtain verbal consent to screen the potential participant for initial eligibility and inform participants that questions may address traumatic experiences and reactions. The screening questions will consist of basic contact information, insomnia symptoms, and PTSD symptoms. The screening will also establish any recent or upcoming changes to PTSD or sleep treatment aside from potential treatment for sleep apnea via the Sleep Clinic, as well as screen for exclusion criteria of recent substance use disorder, psychosis or manic episode within last 5 years, acute suicidality requiring alternate treatment, night shift or rotating shift work, lack of stable housing, and pregnancy. \*This is solely for research purposes.

If the Veteran's sleep study took place in 2018 or earlier, we will obtain their weight at time of sleep apnea testing from the medical record and ask the Veteran their current weight. We will also ask them if they currently snore loudly, feel fatigued during the day, have been recently observed to stop breathing while they sleep, and have a history of hypertension. We will then send this information to a SFVA Sleep Medicine provider via encrypted email who will determine if this Veteran would benefit from an updated sleep apnea test and/or other clinical care prior to enrollment in this study. This will facilitate routine clinical care. Consent. Potential participants deemed initially eligible via phone screen will be invited to attend a consent appointment via phone or video. Prior to the appointment, the consent document will be sent via mail, Secure Messaging on MyHealtheVet (if the Veteran has a printer) or email. The RA will review the consent document with the Veteran and emphasize that participation in the study is voluntary and the Veteran's choice to participate or not will not affect their eligibility for standard care in VA. The Veteran will sign a written consent form and return to study staff.

Clinical interview. Trained clinical interviewers will conduct the CAPS-5 interview to establish PTSD diagnosis and SCID-5 interview to establish insomnia diagnosis. This will take place over phone or video. The SCID-5 will also be used to rule out diagnostic exclusion criteria and establish comorbid mental health conditions for data analytic purposes. A brief medication interview will be conducted to obtain information about recent and current medication use. Interviews will be audio-recorded and reviewed by the Stress and Health Research Program's clinical assessment supervisor \*This is solely for research purposes.

Baseline prospective sleep data. Once eligibility is established, the Veteran will be shown how to complete a sleep diary. He or she will then record one week of baseline sleep data. Research staff will email the Veteran a link to enter sleep diary data via Qualtrics. The Veteran's PAP setup appointment (if needed) and treatment schedule will be planned. \*This is for research purposes; however, please note that completing a sleep diary is also part of routine care.

**Actigraphy.** The actigraph is a device worn on the risk to measure time asleep vs. awake. A subset of participants will be asked to wear the actigraph. The information will be used solely for research purposes. It is not part of the treatment.

**Baseline appointment**. The Veteran will complete pre-treatment measures. He or she will be randomized to either AIR or SE. \* Many of the pre-treatment measures are completed as part of routine care, but some are added for research purposes.

**Randomization procedure.** A block-randomization procedure will be used to assign participants to AIR or SE in a 1:1 ratio. Block sizes will be a random permutation of 4 and 6. Statistical consultant [REDACTED] will produce the computer-generated list. Each therapist will have his or her own randomization list. The randomization to treatment is for research purposes.

**Weekly assessment.** At the start of each treatment appointment, the Veteran will complete two self-report questionnaires assessing sleep (ISI and ESS). The Veteran's PAP adherence data and actigraphy data will also be downloaded or requested verbally. A copy of the Veteran's sleep diary will be obtained. At his or her final treatment appointment, the Veteran will be asked to complete a sleep diary to submit at the Post-Treatment

Assessment appointment. In addition, at weeks 1, 3 and 5, the Veteran will complete the primary and secondary functioning outcome measures (WHOQOL-BREF and FOSQ-10.) \*Completion of ISI and ESS, sleep diary data, and PAP adherence are part of routine care and will also be used for research purposes. The additional WHOQOL-BREF AND FOSQ-10 at weeks 1, 3 and 5 are for research purposes.

**Post-Treatment Assessment.** One week following his or her final treatment appointment, the Veteran will attend the post-treatment assessment appointment via phone or video. He or she will turn in the sleep diary with data from the preceding week. He or she will turn in the actigraphy device. The Veteran will complete post-treatment questionnaires. A trained, blinded clinical interviewer will repeat the CAPS-5 interview (current symptoms only) and SCID-5 (insomnia portion only) and inquire about medication changes. The Veteran will complete a brief feedback interview about their treatment experience with study staff. The Veteran's PAP adherence data will be downloaded or provided verbally. \*This is for research purposes.

**3-Month Follow-Up Assessment.** Veterans will complete the 3-month follow-up questionnaires. PAP adherence data will be downloaded or provided verbally. If the Veteran's PAP device does not have a functional modem, the study team will arrange for the Veteran to provide their SD card for data download. The data will be uploaded to the appropriate clinical data monitoring system and the SD card will be returned to the Veteran. Veterans' charts will be checked to track PAP follow-up appointment attendance, if applicable. Veterans will be sent a sleep diary to complete the week prior to this appointment and will submit it at this appointment. \*This is for research purposes. However, review of PAP adherence data at 3-month follow-up is also part of routine care in the Sleep Clinic.

